5.5 Per Protocol Analyses

We will conduct per-protocol analyses for the effect of first-stage randomization groups on primary and secondary outcomes. A per-protocol analysis is of particular importance for the LAF versus RUSF on the 12-week anthropometric recovery outcome, as suboptimal adherence may bias estimates to the null, which is anti-conservative in the non-inferiority design. Nevertheless, for consistency in analyses of first-stage interventions, we will present per-protocol analyses for all primary and secondary outcomes for the MDSF, LAF, and RUSF comparisons. The per-protocol analysis will include participants who take their randomized regimen for at least 75% of days between randomization and 12 weeks and have data (non-missing) for the outcome of interest at 12 or 24 weeks.

Per protocol analyses are not planned for the second-stage interventions due to the superiority testing focus and the nature of the sustained recovery intervention and control interventions.

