- 6) Mean change in skinfold thickness measurements from randomization to 24 weeks: This will be the 24-week skinfold thickness measurements minus the randomization measurement value.
- 7) Severe acute malnutrition (SAM) from randomization to 24 weeks. SAM will be defined as a WLZ < -3 z-score or MUAC <115 mm or the presence of bilateral pitting oedema.
- 8) All-cause mortality from randomization to 24 weeks (randomization) to 24 weeks. Deaths that occur on or before day 168 of follow-up will be counted for the 24-week outcome.
- 9) SAM or All-cause mortality from randomization to 24 weeks. This is a composite outcome of SAM or death; if SAM occurs first the date of SAM measurement will be used to define the time period. SAM will be defined as a WLZ < -3 z-score or MUAC <115 mm or the presence of bilateral pitting oedema at any follow-up visit. Deaths that occur on or before day 168 of follow-up will be counted for the 24-week outcome.
- 10) Any hospitalization to 24 weeks: Hospitalization from any cause will be defined as a stay in a health facility >24 hours.

3.3 Trial Sample Size

The trial sample size was based on sample size calculations for the primary outcome analyses. The sample size required for the analysis of non-inferiority of LAF as compared to RUSF on 12-week anthropometric recovery was the largest and therefore determined the overall trial sample size.

Primary Comparison #1- LAF vs RUSF on 12-week anthropometric recovery (non-inferiority): There is some evidence that justifies a non-inferiority comparison between LAF and RUSF. A meta-analysis on the management of acute malnutrition in LMICs suggests no difference in recovery from moderate wasting when standard RUSF was compared to local or homemade food, although this is considered low-quality evidence from only two studies.

The choice of non-inferiority margin was based on the judgment of clinical and public health importance of differences in the primary outcome (in our case, anthropometric recovery by 12 weeks of treatment). The investigator group and WHO staff determined that if the recovery rate with one treatment option was 60% and a non-inferiority margin of a risk difference of -5% is appropriate.

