Based on assumptions of 1:1 randomization, 90% power, a one-sided α =0.025 (0.05/2 for multiple comparisons), 5% loss to follow-up/missing data, and that 60% of participants would have 12-week anthropometric recovery outcome in the RUSF and LAF arms, we would require 2,120 participants in each intervention group. As the rate-limiting randomization #1 sample size, the trial 2,120 participants are enrolled in each of the three first-stage randomization interventions, totaling 6,360 total participants in the trial.

Primary Comparison #2: MDSF vs RUSF on 12-week anthropometric recovery (**superiority**): This hypothesis is based on the evidence from a proof-of-principle study conducted in Bangladesh, which showed that MDSF is better than RUSF in promoting growth. We anticipate that 60% of enrolled children will achieve anthropometric recovery within 12 weeks of enrolment in the RUSF group (comparison group). Based on an enrollment of 2,120 per intervention arm, 1:1 randomization, an α of 0.025 (0.05/2 due to multiple comparisons), and 5% loss to follow-up/missing data, we will have 90% power to detect a relative risk of 1.09 for 12-week anthropometric recovery for MSDF as compared to RUSF.

Primary Comparison #3 MDSF vs RUSF on 24-week sustained anthropometric recovery (superiority): This hypothesis is also based on the evidence from a proof-of-principle study conducted in Bangladesh, which showed that MDSF is better than RUSF in promoting growth.

We anticipate that 40% of enrolled children in the second randomization, therefore 24% overall will achieve 24-week sustained anthropometric recovery in the RUSF group (comparison group). Based on an enrollment of 2,120 per arm, 1:1 randomization, an α of 0.025 (0.05 / 2 due to multiple comparisons), and 10% loss to follow-up/missing data, we will have 90% power to detect a relative risk of 1.21 for 24-week sustained anthropometric recovery for MSDF as compared to RUSF.

Primary Comparison #4 LAF vs RUSF on 24-week sustained anthropometric recovery (**superiority**): We believe that the LAF group could have more sustained recovery than RUSF because it has higher acceptability, lower likelihood of displacing usual diet and breastfeeding, and an easier transition to giving adequate home foods to the child in phase 2 after recovery has been achieved.

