We will report the proportion of participants who reached 12-week anthropometric recovery by LAF and RUSF arms. We will use generalized linear models with a binomial distribution and identity link function to produce risk difference estimates for the LAF arm compared to the RUSF arm. Due to stratified randomization by study site, we will include a fixed effect for the study site in the model. The lower bound of the one-sided 97.5% confidence interval (to account for multiple comparisons) of the risk difference arm will be compared with the prespecified noninferiority margin of -5% to assess non-inferiority. We will also present a p-value for non-inferiority, with a p-value <0.025 considered statistically significant. Two-sided 95% confidence intervals will be presented, which have an upper boundary equivalent to a one-sided 97.5% confidence interval.

iii. MDSF vs RUSF on 24-week sustained anthropometric recovery (superiority): This analysis will utilize data from visits during the first 12 weeks in addition to the 24-week visit. Sustained anthropometric recovery is defined by 12-week anthropometric recovery and continued recovery at the 24-week visit.

If a participant does not complete any follow-up visits at or before the 12-week visit (no 12-week follow-up data), they will be excluded from the analysis (complete case). Individuals who reached anthropometric recovery at 12 weeks but do not have anthropometric data at 24 weeks (loss to follow-up/missing data, death, withdrawal) will also be excluded from the analysis (complete case). Individuals who did not reach anthropometric recovery by 12 weeks will be analyzed as not having met 24-week sustained recovery, regardless of completion of the 24-week visit, as by definition, they will not have met sustained recovery.

We will report the proportion of participants who reached sustained anthropometric recovery at 24 weeks by intervention arm. We will use a log-binomial regression model to present the relative risk (RR) of 24-week sustained anthropometric recovery for the MDSF arm compared to the RUSF arm. Due to stratified randomization by study site, we will include a fixed effect for the study site in the model. We will present the relative risk, 97.5% confidence intervals, and a p-value <0.025 will be considered statistically significant (to account for multiple comparisons).

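### The per-protocol check on LAF non-inferiority selects children by adherence and states no adjustment for who adheres

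*SAP*

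**What the plan says.** - **Decision rule.** Section 4.2 makes intention-to-treat the primary analysis, and 4.3 restricts it to complete cases. In 5.2 ii, the lower confidence bound from a binomial identity-link model with a site term is the deciding figure: the bound "of the risk difference arm will be compared with the prespecified noninferiority margin of -5% to assess non-inferiority". No second analysis set is named.
- **The acknowledged risk.** Section 5.5 gives the per-protocol analysis particular importance for this comparison, because "suboptimal adherence may bias estimates to the null, which is anti-conservative in the non-inferiority design".
- **The check.** The per-protocol set is children who took the randomized regimen on at least 75% of days to week 12 and have outcome data. Section 5.5 commits to presenting the results. It states no model, no adjustment or weighting for adherence, and no way to read a disagreement with ITT.
- **Adjustment planned elsewhere.** Section 4.3 has inverse probability weighting for differential loss to follow-up. Section 5.4 adjusts for chance baseline imbalance. Neither is linked to adherence.
- **A hint on acceptance.** In 3.3, Primary Comparison #4, LAF is expected to sustain recovery better because "it has higher acceptability, lower likelihood of displacing usual diet and breastfeeding".

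**The concern.** Randomization makes the full arms comparable, but not the subsets that adhere. If one food is easier to give, its per-protocol group retains children whom the other arm's group loses. If those children recover less often for reasons unrelated to the food (illness, household circumstances, feeding difficulties), the per-protocol difference mixes the food effect with that selection.

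This matters most for LAF versus RUSF, because it is the comparison for which the SAP relies on per-protocol results to show whether ITT has been diluted. A shift against LAF could cast doubt on a sound non-inferiority result. A shift in its favour could appear to confirm a result that rests on dilution. Either way, a reader with only the unadjusted version cannot separate selection from effect.

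**Working it through.** **Inputs from the SAP (section 3.3).** Margin: "a non-inferiority margin of a risk difference of -5% is appropriate". Design: "90% power, a one-sided α =0.025 (0.05/2 for multiple comparisons), 5% loss to follow-up/missing data". Rates: "60% of participants would have 12-week anthropometric recovery outcome in the RUSF and LAF arms". Size: "we would require 2,120 participants in each intervention group".

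**1. The plan's own figure.** Evaluable n per arm = (1.960 + 1.282)² × (2 × 0.60 × 0.40) / 0.05² = 2,018. Allowing for 5% loss gives 2,125 (dividing by 0.95) or 2,119 (multiplying by 1.05). The stated 2,120 reproduces. With 2,120 × 0.95 = 2,014 evaluable per arm, SE = √(0.48/2,014) = 1.54 points, and power is Φ(5/1.54 − 1.96) = 90%.

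**2. Whether dilution is worth checking.** Assume LAF is 5 points worse when eaten and non-adherers show no arm difference. The ITT difference is then −5 × adherence. P(declare non-inferiority) = Φ((5 − 5 × adherence)/SE − 1.96), with SE about 1.55 points:
- 100% adherence: 2.5%
- 90%: 5.1%
- 80%: 9.4%
- 70%: 16.0%

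The SAP's reason for a supportive check is therefore sound. Treating every non-adherer as receiving no effect makes these figures pessimistic, since a child below 75% of days may still eat much of the food.

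**3. Selection in the unadjusted per-protocol set.** All inputs here are assumed. Let a be the share meeting the 75% rule in an arm, and let adherers recover g points more often than non-adherers for prognostic reasons, with 60% recovery overall. Then:

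per-protocol recovery = 60 + g(1 − a)

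shift (LAF − RUSF) = g(a_RUSF − a_LAF)

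The middle columns take equal foods with LAF better accepted. The right-hand columns reverse the adherence shares and make LAF truly 5 points worse, where a valid test would pass in 2.5%.

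| Adherence, higher / lower arm | g | Shift if LAF is higher | Per-protocol passes, equal foods | Shift if RUSF is higher | Per-protocol passes, LAF truly −5 |
|---|---|---|---|---|---|
| 90% / 80% | 10 | −1.0 | 67% | +1.0 | 9% |
| 90% / 80% | 15 | −1.5 | 56% | +1.5 | 14% |
| 90% / 80% | 20 | −2.0 | 44% | +2.0 | 22% |
| 90% / 70% | 10 | −2.0 | 41% | +2.0 | 21% |
| 90% / 70% | 15 | −3.0 | 21% | +3.0 | 41% |
| 90% / 70% | 20 | −4.0 | 9% | +4.0 | 64% |

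First row, LAF higher: RUSF 62% of 1,611 and LAF 61% of 1,813. SE = √(0.62 × 0.38/1,611 + 0.61 × 0.39/1,813) = 1.67 points. Φ((5 − 1)/1.67 − 1.96) = 67%.

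First row, RUSF higher: RUSF 61% of 1,813 and LAF 62 − 5 = 57% of 1,611. SE = 1.68 points. Φ((5 − 4)/1.68 − 1.96) = 9%.

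With equal adherence and the same g in both arms the shift is zero.

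**4. A second model, as a cross-check.** Assume equal foods; 80% of children adhere to either food, 10% only to LAF and 10% to neither; recovery 64%, 50% and 38%. Overall recovery is 0.8 × 64 + 0.1 × 50 + 0.1 × 38 = 60%. RUSF per-protocol is 64.0%. LAF per-protocol is (0.8 × 64 + 0.1 × 50)/0.9 = 62.4%. The difference is −1.6 points, SE 1.65, and the chance of passing is Φ((5 − 1.56)/1.65 − 1.96) = 55%.

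**The case against.** **ITT as the deciding set is legitimate.** The objectives in 2.2 ask about the effect of the foods when given to children, and failure to eat a food is part of the effect of giving it. The SAP names the risk, fixes a per-protocol threshold in advance and commits to showing the result. This stands.

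**A dual-pass rule does not follow.** A reader might infer that non-inferiority should require both ITT and per-protocol to clear −5%. That is one convention among several, and it would give a veto to an analysis that is itself open to bias. Power would fall below the stated 90%. With no selection, per-protocol power alone caps it at Φ(5/1.63 − 1.96) = 87% if 90% of each arm qualify, and Φ(5/1.73 − 1.96) = 83% if 80% do. In the model of step 4 the cap is 55%. The sample size allows for 5% missing data and nothing for non-adherence.

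**The direction is uncertain.** The only hint in the SAP favours LAF on acceptability, which would push per-protocol against LAF and so be conservative for non-inferiority. The false-pass figures need the opposite pattern. The hint is also a rationale for 24-week superiority and does not forecast who meets the 75% rule. So it does not show that the retained groups must differ, whatever cut-off is used.

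**The inputs are assumed.** This stands. The adherence shares and recovery gaps are illustrations, because the SAP gives none. That 5.5 uses no adjustment beyond the site term is also read from its silence.

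**Conclusion.** The point holds as a weakness of the supportive analysis. The per-protocol comparison on which 5.5 relies to detect dilution conditions on adherence after randomization and states no adjustment for its predictors. Under the assumed inputs the distortion is roughly 1 to 3 points of a 5-point margin, reaching 4 at the most extreme combination tried. It can run in either direction, and it vanishes if adherence and the prognostic gap are the same in both arms.

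Three stronger readings are not supported:
- The SAP does not say that its ITT analysis is anti-conservative. It says suboptimal adherence may bias it that way, so the size depends on the adherence reached.
- Deciding on ITT alone is not an error.
- The sample size is not wrong. It reproduces.

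**What to change.** Add to section 5.5, for LAF versus RUSF on 12-week recovery:

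*The per-protocol risk difference will also be estimated with inverse-probability-of-adherence weights. The probability of meeting the 75% rule will be modelled separately in each arm on site, age, sex, WLZ, MUAC, enrolment criterion and diarrhoea at baseline. Robust standard errors will be used, and the lower bound will be compared with −5%. The unweighted version will be shown beside it. The weighted version is the main supportive check on the ITT conclusion. Any disagreement with ITT will be reported as a limitation of the non-inferiority claim.*

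Section 5.2 ii stays as it is, with ITT deciding. All the listed variables already appear in the SAP as enrolment measures, stratification or subgroup factors, so no new data are needed.

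Costs: modest extra programming and somewhat wider intervals than the unweighted version. The weights remove only the selection that these baseline variables predict, so the result rests on there being no unmeasured predictors of both adherence and recovery. The text should say so. The wording is best settled before results by arm are known.

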5.6 Exploratory Analyses of Potential Effect Modifiers

We will explore the effect modification of the ITT treatment effects on the *primary outcomes* for Phase 1 and Phase 2 interventions by:

- 1) Site region (South Asia [Bangladesh, India, Pakistan] vs sub-Saharan Africa [Tanzania and Mali]
- 2) Infant age at enrollment (6 to <12.0 months vs 12.0 to 24 months)
- 3) Infant sex (male versus female)
- 4) MAM diagnosis type (WLZ only, MUAC only, both WLZ and MUAC).
- 5) Diarhrea at baseline (Diarrhea vs no diarrhea)

Due to the exploratory nature of these analyses, we will not adjust for multiple comparisons but rather recognize there is a risk of type II error. In terms of statistical analyses, the same general modeling approaches will be used for the primary outcomes but will include interaction terms between treatment and the effect modifier of interest. The statistical significance of effect modification will be assessed with the likelihood ratio test.

5.7 Harms

All severe adverse events (SAEs) by trial arm will be reported in the primary manuscript by treatment arm. We will also report anaphylaxis reactions by intervention arm.

